4.2 Justification for dose

This project is designed to evaluate the potential use of fractional dose and heterologous booster regimens for individuals who have previously received two doses of Covid-19 vaccine. The fractional dose has advantages for the individual and the broad community. At an individual level, the likelihood of moderate adverse reactions is reduced by the use of a fractional dose. Existing data suggests that immunogenicity and effectiveness will be maintained, but this will be evaluated early in the project and if immunogenicity proves to be inadequate this will be addressed according to the recommendations of the DSMB. At a national and global level, the approach carries the potential to greatly expand the availability of Covid-19 vaccine, helping to correct the inequity that currently characterises the global Covid-19 situation.

4.3 Trial population

The trial population will be adults 18 years and older who have received two doses of Covid-19 vaccines, either Sinopharm (*BBIBP-CorV*[®]) AstraZeneca (ChAdOx1-S, *Vaxzevria*[®]) or Sputnik V (Gam-COVID-Vac[®]) at least 6 months prior. There will be no upper age limit.

Procedures will be implemented to ensure participants of all ages (aged 18 and above) are included and that there is an even age distribution (<50 and \geq 50 years) in each group.

4.4 Eligibility criteria

If informed consent is granted, study staff will ensure that all the eligibility criteria are met. Potential participants must meet all the inclusion criteria and none of the exclusion criteria to be eligible.

4.4.1 Inclusion criteria

Each participant must meet all the following criteria to be enrolled in this trial:

- 1. Have completed two doses of Sinopharm, AstraZeneca or Sputnik vaccines with the recommended schedule at least 6 months prior to the date of enrolment
- 2. Willing and able to give written informed consent
- 3. Aged 18 years or above

4. Willing to complete the follow-up requirements of the study

Note that subjects with comorbidities other than those listed below as contraindications will be included. Pregnant women or women who may become pregnant will be included.

4.4.2 Exclusion criteria

Potential participant meeting any of the criteria below will be excluded from this trial:

- 1. Received 3 doses of COVID-19 vaccine
- 2. Received 2 doses of COVID-19 less than 6 months prior to the start of the trial
- 3. Currently on immunosuppressive medication or anti-cancer chemotherapy
- 4. Known HIV infection
- 5. Congenital immune deficiency syndrome
- 6. Has received immunoglobulin or other blood products in the 3 months prior to vaccination
- 7. Study staff and their relatives
- 8. Have a history of a severe allergic reaction to any COVID-19 vaccines or have a medical exception to receiving further COVID-19 vaccines

Symptomatic potential participants (cough, sore throat, fever or other symptoms) or those who have tested positive (on PCR or RAT) or are waiting for a SARS-CoV-2 test result will not be enrolled. Such potential participants will be asked to return once their symptoms have resolved and their SARS-CoV-2 test is negative if they were tested.

4.5 Lifestyle considerations

Not Applicable.

4.6 Screen failures

Screen failures are defined as participants who consent to participate in the trial but are found during screening procedures to be ineligible. They, therefore, do not receive the intervention and are not randomised. We anticipate that there will be very few screen failures due to the minimal inclusion/exclusion criteria.

4.7 Recruitment and identification of potential participants

The study will be offered to attendees at District Health centres and hospitals to those who previously attended the clinics for their priming vaccinations. Those interested will be provided with the participant information sheet and consent form (PICF) and a member of the research team will be available to answer their questions. If recruitment is slow, the study may be promoted by the Ministry of Health through their daily media briefings. A record of all potential participants will be recorded on a recruitment log. If the potential participant decides not to participate no identifying information will be retained.

4.8 Consent

Informed consent is a process that is initiated prior to the agreement to participate in the trial and continues throughout study participation. Discussion of risks and possible benefits of this vaccination will be provided to the potential participants prior to obtaining informed consent. Trial staff will go through the Informed Consent Form (ICF), which describes in plain language the trial interventions, the study procedures, and the risks and benefits of participation. The ICF will be HREC-approved and the potential participant will be asked to read and review the ICF. The trial staff will then explain the research study further and answer any questions that may arise.

Written documentation of informed consent is required prior to enrolment into the trial. The potential participant will sign and date the final page of the ICF. The trial staff will witness the consent, confirming that the trial has been fully explained and that the participant understands the rationale for the trial and the trial processes. The potential participant will be informed that they are free to withdraw from the trial at any time. A copy of the ICF will be given to the potential participant.

Following or at the 12 month visit, participants will be invited to participate in an extension study with follow-up visits at 18 months and 24 months. They will be asked to sign a new consent form for the extension.

5 INTERVENTION

5.1 Treatment arms

Treatment Arms	Route	Dose
1) Pfizer-BioNTech (BNT162b2, or Comirnaty ®)	IM	Standard Dose - (30µg)
2) Pfizer-BioNTech (BNT162b2, or Comirnaty ®)	IM	Fractional Dose - (15µg)

5.2 Trial Intervention(s)

Pfizer BioNTech (BNT162b2) BNT162b2 is a lipid nanoparticle-formulated, nucleoside-modified mRNA vaccine that encodes trimerised SARS-CoV-2 spike glycoprotein. BNT162b2 encodes the SARS-CoV-2 full-length spike, modified by two proline mutations to lock it in the prefusion conformation and more closely mimic the intact virus with which the elicited virus-neutralizing antibodies must interact. mRNA vaccines use the pathogen's genetic code as the vaccine; this then exploits the host cells to translate the code and then make the target spike protein. The protein then acts as an intracellular antigen to stimulate the immune response. The mRNA is then degraded within days. The vaccine RNA is formulated in lipid nanoparticles (LNPs) for more efficient delivery into cells after intramuscular injection.

5.2.1 Description of trial investigational products

5.2.1.1 Trial Products

	The Pfizer-BioNTech COVID-19 vaccine, BNT162b2, encodes
Active substance	a P2 mutant spike protein and is formulated as an RNA-lipid
	nanoparticle (LNP) of nucleoside-modified mRNA (modRNA).

Trade or Generic name	Pfizer-BioNTech (BNT162b2, or Comirnaty®)
Decage form	Liquid for injection – standard dose is 0.3ml containing $30\mu g$;
Dosage form	fractional dose is 0.15ml containing 15ug.
Route of administration	Intramuscular injection

5.2.2 Dosage

The standard dose of Pfizer BioNTech COVID-19 vaccine is 30µg contained in 0.3ml of the diluted vaccine and is currently the standard dose that is used for a booster. A half dose is 15 µg contained in 0.15ml of the diluted vaccine. Each pack of the Pfizer BioNTech vaccine contains 195 vials with 5 standard doses per vial (975 doses per pack). It is supplied with 0.9% sodium chloride diluent for injection plastic ampoules.

5.2.3 Dose modification

Dose modification is not permitted and must be given as per randomisation.

5.2.4 Storage, preparation, dispensing and administration of trial drug

All study vaccines will be stored at the central vaccine storage building at the National Center for Communicable Diseases (NCCD) and will be stored in accordance with the manufacturers' recommendations. See below:

• The Pfizer BioNTech vaccine should be stored at -70°C +/- 10°C and has shelf life of 6 months. Once thawed, the vaccine may be stored for 31 days at 2-8°C.

Vaccine accountability, storage, shipment, and handling will be in accordance with relevant SOPs and forms.

5.2.5 Product accountability

The trial vaccines will be provided by the Ministry of Health at District Health centres and hospitals. Study nurses will collect supplies each day and return any unused vaccines at the end of the day. The study nurses will ensure that storage requirements are maintained. Study vaccines will be administered by unblinded vaccinators, who will maintain blinding such that those evaluating reactogenicity are kept blinded during the first week post-vaccination.

The unblinded vaccinators will keep accurate records regarding when and how much trial vaccine is dispensed and used for each participant in the trial. Reasons for departure from the expected dispensing regimen will be recorded. At the end of the trial, there will be final reconciliation of trial vaccine received, dispensed, consumed, and returned. Any discrepancies will be investigated, resolved, and documented by the trial team. Unused trial vaccines will be destroyed in compliance with applicable regulations.

Detailed information regarding product accountability will be provided in an SOP.

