	* Subjects and assessors will be bli	nded to the vaccine dose for one week	
	following administration, and labor	atory staff will be blinded to vaccine	
	dose associated with specimens.		
	Primary vaccine	Booster vaccines	
	Sinopharm (BBIBP-CorV ®)	1 Pfizer-BioNTech (BNT162b2, or	
		Comirnaty [®]) Standard dose (30µg)	
	n= 200		
	2 Pfizer-BioNTech (BNT		
	Comirnaty®) Fractional dose		
	(15µg) n= 200		
	AstraZeneca (ChAdOx1-S, or 3 Pfizer-BioNTech (BNT162b2, or		
	/axzevria®) Comirnaty®) Standard dose (30µg)		
	n= 100		
	4 Pfizer-BioNTech (BNT162b2, or		
	Comirnaty®) Fractional dose		
	(15µg) n= 100		
	Sputnik V (Gam-COVID-Vac®) 3 Pfizer-BioNTech (BNT162b2, or		
	Comirnaty®) Standard dose (30µ		
		n= 100	
		4 Pfizer-BioNTech (BNT162b2, or	
		Comirnaty®) Fractional dose	
		(15µg) n= 100	
OBJECTIVES	Primary objectives –		
	• To assess and compare the immune response measured as		
	binding antibodies (IgG ELISA) following fractional versus		
	standard doses of Pfizer vaccine given as single additional dose		
	in adults 18 years and older in Mongolia who have been		
primed through previous vaccination with Astra Zer Sinopharm or Sputnik vaccines. (Timepoint – 28 da		accination with Astra Zeneca,	
		nes. (Timepoint – 28 days post	
	vaccination)		

	 To assess the rate and severity of the reactogenicity within one-week post-booster for each schedule evaluated (Timepoint – daily, for seven days post vaccination) Secondary objectives - (timepoint – 6,12, 18, and 24 months for all) To compare the duration of immunity, both humoral and cellular, over 24 months for fractional vs standard booster doses of the vaccines listed. To evaluate the different priming capacities of Sinopharm, AstraZeneca and Sputnik vaccines. To assess the impact of prior natural exposure on boosting regimens. To evaluate the safety of the booster dose regimens 	
	To evaluate the safety of the booster dose regimens	

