4 TRIAL DESIGN

4.1 Overall design

This clinical trial will be a single blind, randomised study to determine the immunogenicity and reactogenicity of booster doses of SARS-CoV-2 vaccines in adults. Both fractional and standard doses will be tested.

The groups are described below. The trial intervention will be a single booster dose of vaccine: -

Primary vaccine	Booster vaccines
Sinopharm (BBIBP-CorV ®)	1. Pfizer-BioNTech (BNT162b2, or Comirnaty®) Standard
	dose (30µg) n= 200
	2. Pfizer-BioNTech (BNT162b2, or Comirnaty®) Fractional
	dose (15µg) n= 200
AstraZeneca (ChAdOx1-S, or	3. Pfizer-BioNTech (BNT162b2, or Comirnaty®) Standard
Vaxzevria®)	dose (30µg) n= 100
	4. Pfizer-BioNTech (BNT162b2, or Comirnaty®) Fractional
	dose (15µg) n= 100
Sputnik V (Gam-COVID-Vac®)	5. Pfizer-BioNTech (BNT162b2, or Comirnaty®) Standard
	dose (30µg) n= 100
	6. Pfizer-BioNTech (BNT162b2, or Comirnaty®) Fractional
	dose (15µg) n= 100

The trial intervention will be given 6 or more months after the primary vaccine schedule. The groups size will be either 200 (Sinopharm groups) or 100 (AstraZeneca and Sputnik groups) individuals with an even spread of participants above and below 50 years in each group. The Sinopharm vaccinee impact is of greater importance to Mongolia as this is the main vaccine used for the primary series in Mongolia. In addition, Sinopharm is the least effective of the 3 vaccines used, so we expect to see evidence of more breakthrough cases and therefore a wider range of pre-booster immunity levels. The trial will be conducted at multiple sites (health centres, hospital or vaccination clinics) in Ulaanbaatar and provincial sites.

The trial will be single blind. The participants and those evaluating reactogenicity will be blinded to the vaccine dose allocation for the first 28 days following vaccination. After that, both the clinical investigators and potentially participants will be aware of their investigational product dose allocation. Immunologists and laboratory staff will remain blinded to the investigational product dose allocation.

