6.1 Concealment mechanism

Randomisation will be stratified according to age (<50 and \geq 50 years) and primary vaccine (*BBIBP-CorV*[®] or *Comirnaty*[®]). Using REDCap the participants will be randomised to one of two groups in a 1:1 dose allocation ratio. (see table below).

Primary vaccines	Age	Booster vaccine	Dose given
Sinopharm,	<50	Pfizer-BioNTech	30µg
AstraZeneca, or		Pfizer-BioNTech	15µg
Sputnik V	>=50	Pfizer-BioNTech	30µg
		Pfizer-BioNTech	15µg

Study staff (unblinded vaccinator) involved in administering the vaccine will use REDCap to receive the information on the participant's randomisation number and vaccine dose so they will be aware of which vaccine the participant is receiving. The participants themselves will remain blinded to their vaccine dose (until day 28 post vaccination). Study staff involved in assessing reactogenicity will be blinded to each participant's vaccine dose until 28 days post vaccination, as this variable will be hidden in REDCap for blinded study staff. Study staff involved in assessing immunogenicity outcomes will remain blinded during the analysis of specimens.

Vaccines will be prepared out of sight of the participant and the blind will be maintained by applying masking tape over the vaccine syringe, so the study participant can't see the volume.

Only the study nurse (unblinded vaccinator) administering the vaccine will be aware of which vaccine is given to the study participant.

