6.2 Breaking of the trial blind 6.2.1 On trial

The study will be blinded for the first 28 days only. In the unlikely event that it becomes necessary to unblind during this period that decision will be taken by the PI, and the subject and physicians who may be caring for the subject will be made aware of the dose allocation.

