7.2.2 Visit 3 (Day 7)

Study staff will contact the participant by phone one week after vaccination. If participants have a hard copy card study staff will ask participants to read the details over the phone or send a picture of their hard copy diary card (with the name obscured) for review. If the participant completed the REDCap

diary card, study staff will review it with them to confirm that all symptoms are captured. Study staff will also document any significant, unexpected, serious or unusual adverse events on the AE CRF.

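### The protocol states two blinding periods, one week and 28 days; under the one-week text, blinding is not assured for late diary reviews or for Day 8-28 adverse event assessment

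*Protocol*

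**What the plan says.** Two places in the protocol set one week. The synopsis footnote on the single-blind design has participants and assessors blinded "to the vaccine dose for one week". Section 5.2.5 (Product accountability) directs the unblinded vaccinators to preserve the blind so that "those evaluating reactogenicity are kept blinded during the first week post-vaccination".

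The other places set 28 days or the Day-28 visit:

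- Section 4.1 has participants and reactogenicity evaluators "blinded to the vaccine dose allocation for the first 28 days following vaccination".
- Section 6.1 blinds reactogenicity staff to each participant's "vaccine dose until 28 days post vaccination, as this variable will be hidden in REDCap for blinded study staff".
- Section 6.2.1 states: "The study will be blinded for the first 28 days only".
- Section 7.2.3 has the participant told the dose at Visit 4 (Day 28).
- SAP 3.5 blinds participants and reactogenicity assessors up to the Day-28 visit.

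All of these are current text. SAP 6.1.1 lists departures from the protocols, including one on the blinding of statisticians, but does not mention this conflict.

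**The concern.** The reactogenicity diary covers seven days, so one week of blinding might seem enough. The staff contribution to those data runs later. For Visit 3 the protocol says: "Study staff will contact the participant by phone one week after vaccination". The schedule allows three extra days. At that call staff hear or view paper diary entries, or go through the electronic diary with the participant. Paper cards come in for data entry at Day 28 (7.2.1), and new information on solicited reactions is also recorded then (7.2.3).

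One of the two primary endpoints is at stake: grade 3 or 4 solicited reactions within 7 days (SAP 5.1.2). Several of its grades turn on judgement, for instance whether a symptom stopped daily activity. Unsolicited events to Day 28 are tabulated by severity and by causality (SAP Table 8), and protocol 8.4 and 8.5 leave both to the assessor's judgement. The protocol expects fewer reactions with the fractional dose (2.4.1, 4.2), so dose knowledge could push these assessments in a foreseeable direction.

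**Working it through.** There is no figure in the plan to reproduce. The check sets the texts side by side and counts days.

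**Side by side**

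| Place | Who is named | End of blinding |
|---|---|---|
| Protocol synopsis footnote | participants, assessors | one week |
| Protocol 5.2.5 | reactogenicity evaluators | one week |
| Protocol 4.1 | participants, reactogenicity evaluators | 28 days |
| Protocol 6.1 | participants, reactogenicity staff | 28 days, dose field hidden in REDCap |
| Protocol 6.2.1 | the study | 28 days |
| Protocol 7.2.3 | participants | told at Visit 4 |
| SAP 3.5 | participants, reactogenicity staff | Day-28 visit |

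**Inputs for the day count**

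- Vaccination is Day 0 (SAP 6.8). I take the first week to end with Day 7.
- Visit 3 is Day 7 with a window of +3 days, and Visit 4 is Day 28 with a window of +7 days (protocol 7.1).
- Unsolicited events are collected for 28 days (protocol 3.2.2).

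**Results**

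1. Visit 3 falls between Day 7 and Day 7 + 3 = Day 10. A call on Day 8, 9 or 10 comes after the blinding that the one-week text guarantees. Under the 28-day text every permitted day is blinded.
2. Unsolicited event collection outside the guaranteed week: Days 8 to 28 inclusive = 28 - 8 + 1 = 21 days, and 21/28 = 75% of the collection period. This counts calendar days only. It does not estimate how many events fall there or how many would be assessed differently.
3. The longer period is itself stated in two ways. Visit 4 can fall as late as 28 + 7 = Day 35, so 28 days and the Day-28 visit can differ by up to 35 - 28 = 7 days.
4. Section 7.2.3 places adverse event documentation and disclosure of the dose at the same visit and states no order between them. Moving the end-point to that visit therefore does not by itself protect what is recorded there.

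No sample size or power figure in protocol 11.1 depends on the blinding period.

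**The case against.** The case for leaving this as a minor edit is substantial. The sections that govern blinding agree on 28 days, and 6.1 supplies the mechanism: the dose field is hidden and only the vaccinator knows the allocation. Section 6.2.1 reserves earlier unblinding to a decision by the principal investigator. The one-week statements sit in a synopsis footnote and a product accountability clause, and neither describes an unblinding step. Keeping evaluators blinded for a week is also literally satisfied by keeping them blinded for 28 days. The diary is filled in by participants during the first week. The Day-28 update on solicited reactions chiefly concerns matters such as resolution, which does not settle whether a grade 3 or 4 reaction occurred.

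Most of this stands, and it limits the consequence. A reader might infer from the one-week text that every unsolicited event from Day 8 to Day 28 was assessed by staff who knew the dose, or that 75% of events are affected. The documents support neither reading. No section discloses the dose to anyone on Day 8, and 5.2.5 names only reactogenicity evaluators. A reader might also infer that a formal comparison of the arms is compromised. The primary reactogenicity endpoint is descriptive (SAP Table 6 and 6.1.2), and so is every safety endpoint in SAP Table 8.

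The objection does not remove the contradiction. The synopsis footnote refers to participants and assessors generally, and 5.2.5 is the text addressed to the people who hold the allocation. The one-week wording may be left over from another version, but the documents do not say so.

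**Conclusion.** The inconsistency is real, unresolved in the documents, and worth correcting. Its size is limited. If the one-week text were followed, blinding would not be assured for a Visit 3 diary review on Days 8 to 10, or for severity and causality assessment of unsolicited events on 21 of the 28 collection days. This rests on counting the first week through Day 7 and on reading the one-week statements as the full period protected. Whether anyone was in fact unblinded early cannot be determined from the documents.

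The exposure is confined to descriptive reactogenicity and safety results. The non-inferiority conclusion on seroresponse is not affected, because laboratory staff remain blinded to dose under both versions.

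**What to change.** 1. Amend the synopsis footnote and section 5.2.5 to agree with 4.1, 6.1, 6.2.1, 7.2.3 and SAP 3.5. Use a single end-point throughout: until the Day-28 visit.
2. State in 7.2.3 that adverse event documentation at the Day-28 visit is completed before the dose is disclosed.
3. The synopsis says recruitment is complete, and 7.2.6 refers to participants already past their 12-month visit, so rewording cannot change how blinding was conducted. Confirm from REDCap access records which blinding period was applied, and state it in the study report beside the reactogenicity and Day-28 safety tables. If one week was applied anywhere, or the records cannot settle the matter, the report should say so.

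The cost is two wording corrections, matching end-point wording in the sections that say 28 days, one sentence on the order of steps at Visit 4, a check of existing records and a short statement in the report. No new data or analyses are needed.

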5.2.6 Excluded medications and treatments

There are no excluded medications or treatments apart from those associated with exclusions listed in section 4.4.2.

5.2.7 Concomitant therapy

Concomitant medications taken by participants during the study will be documented, as outlined below, as part of the safety review procedures.

From the study start until 24 months, only the following medications of interest will be recorded:

- Any vaccine.
- Any investigational products.
- Immunosuppressive therapies.
- Therapies taken for suspected or confirmed COVID-19

Concomitant medications records will include the drug name, total daily dose, route of administration, start and stop date of administration, and indication for use.

